6.5 Interim Analysis and Adaptive Design

There is no planned interim analysis.

6.6 *Timing of Final Analyses*

Data summary and statistical analysis will commence after all subjects have completed study Visit 7 (or discontinued prior to Visit 7) and the study database is cleaned and locked.

6.7 *Multicenter Study*

This is a multicenter study. The primary analysis will have all sites pooled. Where applicable, analysis adjusting for site effect or analysis evaluating homogeneity across sites may be carried out. If conducted, small sites (defined as those with sample size <9 ITT subjects/site) will be pooled with larger sites based on the geographic proximity.

6.8 *Multiple Comparisons/Multiplicity Adjustment*

Because of the early termination of the 18 mg arm based on the external data, there will be no formal hypothesis test and statistical comparison between the 18 mg arm and the placebo arm for any of the efficacy endpoints. Thus, there is no multiplicity adjustment due to the multiple dose arms to placebo comparisons with respect to the primary and key secondary endpoint analysis. Multiplicity adjustment for the multiple endpoints with respect to additional secondary end points will be carried out in a fixed sequential gate-keeping approach. The test of the null hypothesis of 36 mg vs placebo for additional secondary endpoints from one endpoint to the next endpoint will be carried out in such a way that the test of the subsequent endpoint will be conducted if and only if the test rejects the null hypothesis for the previous additional secondary endpoint. If any test fails to reject the null hypothesis with respect to a certain additional

secondary endpoint then there will be no test of hypothesis with respect to all subsequent additional secondary endpoints and these tests will all be considered failure.

6.9 *Examination of Subgroups*

In addition to the analysis adjusted for the confounding effects by the covariates (see Section 6.3), primary and key secondary efficacy variables will be summarized by subgroup to explore the heterogeneity of the treatment effect across subgroups. Subgroups are defined as follows:

- Gender (Male, Female)
- Age (6-9, 10-12)
- Race (White, Non-white)

7 STATISTICAL ANALYSIS

7.1 Analysis Populations

The population of "all enrolled subjects" consists of all those screened subjects who meet the requirements for study participation and are entered in the Baseline period (i.e., distributed IA diary) of the study. The population of "all randomized subjects" consists of all those enrolled subjects who complete the Baseline Period, meet the inclusion/exclusion criteria and are randomized.

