# 6.3 Analysis Populations

The population of "all enrolled subjects" consists of all those screened subjects who meet the requirements for study participation and are entered in the Baseline period of the study. The population of "all randomized subjects" consists of all those enrolled subjects who complete the Baseline Period, meet the inclusion/exclusion criteria and are randomized.

Safety Population: will include all randomized subjects who received at least 1 dose of study drug.

Intent-to-Treat (ITT) Population: will include all subjects who received at least 1 dose of study drug and have a baseline and at least 1 valid post-randomization assessment of frequency of IA behaviors based on IA diary entry.

Per-Protocol (PP) Population: will include all of the subjects in the ITT population who completed the treatment period with 80% diary completion compliance and who did not have major protocol deviations.

PK population: will include all subjects in the safety population who had at least one PK sample drawn which had a quantifiable concentration for at least one analyte of interest.

The safety, ITT, PP, and PK populations are based on randomized treatment received.

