3.6 Changes to Analyses Planned in the Protocol

This SAP will be updated as necessary if any changes in the protocol occur due to the expected protocol amendment impacting the SAP.

4 **DEFINITIONS AND DERIVED DATASETS**

Table 1. Terminology and Definition

| Terminology | Definition |
|----------------------------|--|
| Study Medication | SPN-810 or the matching placebo. |
| Study Day | The first dose date (Day 1) is defined as the date on which a subject took the first dose of double-blind study medication (SM), Other study days are defined relative to the Study Day 1. For visits prior to the first dose of the SM, Study Day is calculated as Visit Date – Day 1. For visits after the first dose, Study Day is calculated as Visit Date – Day 1 +1. |
| Enrolled | Subject has provided signed informed consent. |
| Randomized | Subject is assigned with the kit number for the SM. |
| Completer for the Study | Subject who completes the maintenance period (Visit 6). |
| Baseline | Unless specified otherwise, baseline is defined as the non-missing value collected most recent to and before the time of the very first dose of the SM. For example, Visit 3 CGI-S, CHQ-PF28, PSI-4-SF, and SNAP-IV are collected prior to the first dose. Their values are considered baseline for the covariate analysis. |
| Baseline Period | For subject daily IA diaries, on and prior to Visit 3 (inclusive, ≤Day 1). |
| Prior Medication | Medication collected on the Prior/Concomitant Medication CRF, with the start date prior to Study Day 1. |
| Concomitant Medication | Medication collected on the Prior/Concomitant Medication CRF, with end date on/after Study Day 1. |
| Titration Period | For subject daily IA diaries from Visit 3 through Visit 5 (v3< to \leq V5) |
| Maintenance Period | For subject daily IA diaries from Visit 5 through Visit 6 (V5< to \leq V6) |
| Treatment Period | Titration and Maintenance Periods combined |

| Terminology | Definition |
|-----------------|--|

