7.1.1 Safety Population

The safety population will include all randomized subjects who received at least 1 dose of study drug and have at least one post-randomization safety measurements.

7.1.2 *Modified Intent-to-treat (mITT) Population*

The modified intent-to-treat population will include all subjects who received at least 1 dose of study drug and have a baseline IA frequency \geq 6 per week and at least 1 valid post-randomization assessment of frequency of IA behaviors based on IA diary entry. Subjects will be analyzed according to the treatment they were randomized to.

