7.3 Disposition of Subjects

Subject disposition and reasons for screening failure will be summarized for screen-failed subjects (Table 14.1.2.2).

Subject randomization schedule will be listed. Subjects whose randomization codes are unblinded during the conduct of the study will be listed along with the reason for un-blinding (Listing 16.1.7).

The following summaries and listings will be based on all randomized subjects.

Subjects (n and %) who completed and discontinued from the study will be tabulated by the treatment group and study period (titration, maintenance, titration and maintenance combined, and all period combined) for randomized population (Table 14.1.1). The primary reasons for study discontinuation will be included in the tabulation. The primary reasons may include any of the following:

- Subject withdrew consent
- Lost to follow-up
- Administrative reason
- Adverse event
- Investigator decision

- Failure to follow required study procedures
- Other

Also, subject's enrollment will be summarized by study site among ITT population (Table 14.1.2.3).

A data listing will be presented for subject's disposition and reasons for discontinuation (Listing 16.2.1.1).

7.4 *Protocol Deviations*

Protocol deviations will include, but are not limited to

- Non-compliance with any scheduled study visit
- Non-compliance with study treatment
- Prohibited medications
- Non-compliance with study inclusion or exclusion criteria
- Non-compliance with study assessment procedures

Subjects with major protocol deviations will be listed based on all randomized subjects. The listing will include a brief description of the deviation, deviation category, and if applicable, study day when deviation occurred along with other pertinent information (Listing 16.2.1.2).

If warranted, subjects (n and %) with major protocol deviations will be tabulated by treatment group and deviation category for ITT population (Table 14.1.2.4).

Subject's inclusion/exclusion from each analysis population will be listed along with the applicable reasons for exclusion (Listing 16.2.1.3).

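### SAP 7.1 and Protocol 6.3 make eligibility part of being randomised, in conflict with SAP Section 4; taken literally, a dosed but ineligible child leaves the safety, disposition and deviation-listing outputs

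*SAP*

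**What the plan says.** SAP 7.1 and Protocol 6.3 use the same words. The population of *all randomized subjects* consists of "all those enrolled subjects who complete the Baseline Period, meet the inclusion/exclusion criteria and are randomized". Meeting the criteria stands as a condition of its own, beside being randomised.

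The SAP also has a terminology table in Section 4. There, randomised means: "Subject is assigned with the kit number for the SM". It carries no eligibility condition. The same table defines enrolled as "Subject has provided signed informed consent", whereas SAP 7.1 requires entry into the baseline period, so Section 4 and Section 7.1 differ on that term too.

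The phrase defined in 7.1 is then used as a base elsewhere:

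- SAP 7.1.1: "The safety population will include all randomized subjects who received at least 1 dose of study drug" (the SAP adds a requirement for a post-randomisation safety measurement). Protocol 6.3 has the same base: the safety population "will include all randomized subjects who received at least 1 dose of study drug".
- SAP 7.3, on disposition: "The following summaries and listings will be based on all randomized subjects".
- SAP 7.4: "Subjects with major protocol deviations will be listed based on all randomized subjects". Among the deviation types that section names is "Non-compliance with study inclusion or exclusion criteria".

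SAP Appendix 2 labels Table 14.1.1 and Listings 16.2.1.1 to 16.2.1.3 as randomised-population outputs. It labels the adverse-event tables and listings as safety-population outputs.

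**The concern.** Safety reporting should cover every child who was randomised and took study drug, whether or not an entry criterion was later found to have been missed. Here the text that defines the base population carries an eligibility test. A programmer who codes the safety flag from Section 7.1 would drop a dosed violator. One who codes it from Section 4 would keep the child. One SAP therefore supports two different safety sets.

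At stake on the literal reading are three things. The adverse-event, laboratory, ECG and EPS-scale data of a dosed violator would be missing from the safety tables. The disposition table would not account for every child given a kit. Listing 16.2.1.2 would be run on a set that cannot contain the eligibility violations it is meant to show.

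A late-found violation is plausible in this trial. Protocol 4.1.1 requires a qualifying CGI-S at randomisation, yet the Visit 3 list in Protocol 4.2.3 puts randomisation (item 4) before the CGI-S (item 5). That list may not be in time order, so it shows only how such a case could arise.

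**Working it through.** No arithmetic applies and the plan gives no figure to reproduce. The check follows one child, randomised and dosed although ineligible, through each output under the two definitions.

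| Output | Stated base | SAP 7.1 / Protocol 6.3 taken literally | SAP Section 4 |
|---|---|---|---|
| Safety population (SAP 7.1.1), hence the AE tables and AE listings | Randomised and dosed | Out | In, given a post-randomisation safety measurement |
| Disposition: Table 14.1.1, Listing 16.2.1.1 | Randomised | Out | In |
| Listing 16.2.1.2, major deviations | Randomised | Out | In, if the deviation is major |
| Listing 16.2.1.3, reasons for exclusion from populations | Randomised (Appendix 2) | Out | In |
| ITT (SAP 7.1.3) | Dosed, with a valid diary assessment after randomisation | In, if such an assessment exists | Same |
| mITT (SAP 7.1.2) | As ITT, with baseline IA frequency of at least 6 per week | In, if both conditions hold | Same |
| Table 14.1.2.4, major deviations by category | ITT, only if warranted | In, if in ITT, the deviation is major and the table is produced | Same |

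Four things follow.

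1. The first four rows turn entirely on which definition governs, and the SAP does not say.
2. On the literal reading, a dosed violator with diary data is in ITT, and possibly in the primary mITT analysis, but not in the safety population.
3. On the literal reading, a violator who is dosed and stops before any valid diary assessment is in neither ITT nor safety, and reaches none of the outputs in the table.
4. Membership of ITT and mITT does not depend on the disputed wording, so the primary and key secondary analyses are unaffected.

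**The case against.** The strongest reply is that the sentence in 7.1 merely narrates the trial sequence: finish baseline, pass the check at Visit 3, be randomised. Protocol 3.2.2.1 does require the criteria to be re-assessed before randomisation. SAP 7.4 expects eligibility violations among the deviations and lists major deviations on the randomised set, a provision that has no effect for such violations if violators are excluded from that set. With the kit-number definition in Section 4, that reading is reasonable and may be what the authors intended. It stands as far as this: exclusion is not established. It does not remove the defect, because neither document says the clause is descriptive, and 7.1 is the section that defines the exact phrase used by 7.1.1, 7.3 and 7.4. Protocol 7.3 points the other way, stating that an unqualified subject may be ineligible for analysis.

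A reader might infer that the count of eligibility violations must be zero in every output. The documents do not support that. Table 14.1.2.4 is on ITT, which has no eligibility condition. Protocol 6.6 places no population limit on its deviation listings, though SAP Section 1 says the SAP supersedes the protocol's statistical methods.

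It is also fair to say that no data are lost at collection. Protocol 4.2 and SAP 3.2 follow every child randomised and dosed, and SAE reporting in Protocol 5.4.2.1 has no eligibility condition. The issue is which children the tables and listings include.

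**Conclusion.** The definition is wrong as written and should be corrected. SAP 7.1 and Protocol 6.3 contradict SAP Section 4. If 7.1 is followed to the letter, a child randomised and dosed in error leaves the safety population, the AE tables and listings, the disposition outputs and Listings 16.2.1.2 and 16.2.1.3.

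Two stronger statements go beyond the text. One is that such children will certainly be dropped: the competing definition and the Visit 3 reading leave that open. The other is a count of children affected: the documents give no rate of eligibility violations, so any number would rest on an assumed rate. The conclusion needs neither. It rests only on the two definitions and on the outputs that use the defined phrase.

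**What to change.** In SAP 7.1, delete the clause on meeting the inclusion and exclusion criteria, and define *all randomized subjects* as every subject assigned a kit or randomisation number through IWRS, in line with SAP Section 4. Make the same change in Protocol 6.3 at the next amendment. State that dosed violators remain in the safety, disposition and deviation outputs. Handle eligibility violations as protocol deviations and, where major, through the per-protocol exclusion that SAP 7.1.4 already contains.

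The cost is one sentence in the SAP. It needs no new data or subjects, and the ITT and mITT definitions stay as they are.

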7.1.1 Safety Population

The safety population will include all randomized subjects who received at least 1 dose of study drug and have at least one post-randomization safety measurements.

7.1.2 *Modified Intent-to-treat (mITT) Population*

The modified intent-to-treat population will include all subjects who received at least 1 dose of study drug and have a baseline IA frequency \geq 6 per week and at least 1 valid post-randomization assessment of frequency of IA behaviors based on IA diary entry. Subjects will be analyzed according to the treatment they were randomized to.

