# **6** STATISTICAL METHODS

# 6.1 Statistical and Analytical Plans

Tabular summaries of the data collected during the study will be presented to provide a general description of the subjects studied and an overview of the Efficacy, PK and safety results. Data from all sites will be combined in the computation of these summaries and summaries will be presented by treatment group. Continuous variables will be summarized using descriptive statistics (number of subjects, mean, standard deviation [SD], median, and minimum and maximum values). Categorical (nominal) variables will be summarized using frequency tables (number and percentage of subjects in each category).

In addition to tabular summaries, subject data listings, as specified in Sections 16.2 and 16.4 of ICH Guidance E3, will be provided. Additional subject data listings to be provided for this study are listed under the relevant subsections below. All data analyses will be performed by the CRO after the study is completed and the database is released. Statistical programming and analyses will be performed using SAS® and/or other validated statistical software as required.

Complete details of the statistical analysis will be provided in a separate statistical analysis plan (SAP), which will be written, finalized, and approved prior to database lock and will be included in the Clinical Study Report (CSR) for this protocol. The statistical analysis plan will supersede the statistical analysis methods described in this clinical protocol. Any deviation from the statistical plan will be documented and described in the final report. If changes to principal features stated in the protocol are required, these will be documented in a protocol amendment. The final SAP will take into account any amendment to the protocol.

In general, the baseline value for a variable is defined as the last observation prior to the first dose of double-blind study medication, ideally Visit 3, but including the screening value, if necessary.

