# 6.5 Subject Disposition

A disposition of subjects will include the number and percentage of subjects in each of the following categories:

- Subjects in the randomized population
- Subjects in the ITT population
- Subjects treated (safety population)
- Subjects in the PP study population

Within each of the previous categories, the number and percentage of subjects who completed and discontinued from the study will be summarized. The reasons for study discontinuation will also be summarized. The reason for discontinuation may include any of the following:

- Subject withdrew consent
- Lost to follow-up
- Administrative reason
- Adverse event
- Investigator decision
- Failure to follow required study procedures
- Other

Only one (primary) reason for study discontinuation will be recorded for each subject.

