# 6.12 Pharmacokinetic Analyses

# 6.13 Safety Analyses

Evaluation of safety will be performed for the safety population. Safety data that will be evaluated include concomitant medications, AEs, clinical laboratory results, vital signs, ECGs, and findings from the physical examinations. The occurrence of neurological side effects will be assessed by looking at any worsening in scores from Visit 3 to each subsequent visit for each of the Simpson-Angus scale, Barnes Akathisia scale, and AIMS. Suicidal ideation and suicidal behavior will be measured by C-SSRS.

All summary tables related to safety analyses will use the safety population.

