1 INTRODUCTION

The purpose of this statistical analysis plan (SAP) is to ensure the credibility of the study findings by specifying the statistical approaches to the analysis of the data prior to database lock. This SAP covers the planned analyses of all data collected on the eCRFs and diary pages, and will identify handling of data issues. The statistical analysis plan presented in this document will supersede the statistical analysis methods described in the clinical protocol. Any deviations/changes from the planned analyses described in this SAP will be identified, with justification, in the appropriate section of the clinical study report. This SAP is based on the clinical study protocol 810P302, version 7.0, dated 29 March 2019 and its associated electronic case report forms (eCRF).

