7.9 Safety Analyses

Subject safety is assessed by AEs, labs, vital signs, 12-lead ECGs, and findings from the physical examinations. The occurrence of neurological side effects will be assessed by looking at any worsening in scores for each of the Simpson-Angus scale, Barnes Akathisia scale, and AIMS. Suicidal ideation and suicidal behavior will be measured by C-SSRS. All summaries related to safety analyses will use the safety population and will be presented by treatment groups.

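### SAP 7.1.1 narrows the protocol's Safety Population with an undeclared, undefined follow-up condition, so some dosed children could be missing from every safety table

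*SAP*

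**What the plan says.** Protocol 6.3 says the Safety Population "will include all randomized subjects who received at least 1 dose of study drug". The synopsis gives the same definition, and the disposition list in protocol 6.5 uses the term as a synonym for subjects treated. Neither adds a further condition.

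SAP 7.1.1 keeps the dosing requirement and adds a second one: children "who received at least 1 dose of study drug and have at least one post-randomization safety measurements".

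Both documents agree on precedence. SAP section 1 says that the SAP "will supersede the statistical analysis methods described in the clinical protocol", and protocol 6.1 says the same from its side: "The statistical analysis plan will supersede the statistical analysis methods described in this clinical protocol".

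On use, SAP 7.9 states: "All summaries related to safety analyses will use the safety population and will be presented by treatment groups". Protocol 6.13 has the matching rule, "All summary tables related to safety analyses will use the safety population", but there it refers to the wider protocol set.

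SAP 3.6, the section reserved for changes from the protocol's planned analyses, says only that the SAP will be updated if the protocol is amended. It does not mention the safety set.

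**The concern.** A safety set should depend on exposure alone. Once membership also depends on something observed after the first dose, the set is selected on follow-up, and the children most likely to fail are those who took study drug and were then not seen again.

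The clause is also too loose to program consistently. It does not say what counts as a measurement, and it is tied to randomisation rather than to dosing. Two programmers could derive different denominators in good faith.

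The outputs could then disagree. ITT in SAP 7.1.3 needs one dose and one valid post-randomisation diary assessment, and the diary is kept by the caregiver at home. A child with diary entries but no qualifying safety measurement would count for efficacy and not for safety.

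**Working it through.** No figure in the plan bears on this and no calculation was run. The check compares the texts and traces the consequences.

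1. **Membership.** Protocol set: randomised and dosed. SAP set: randomised, dosed and at least one safety measurement after randomisation. The SAP set is therefore the protocol set minus dosed children with no such measurement. It can be smaller but never larger.

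2. **Precedence.** Both documents give it to the SAP, so the narrower set governs.

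3. **Declaration.** SAP 3.6 is silent. The revision history is silent too, although it covers only the step from version 2 to 2.1 and so says less.

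4. **Outputs reached.** In SAP Appendix 2 every Table 14.3.x is titled for the Safety Population. So are Tables 14.1.3.1 to 14.1.3.4 (medical history, prior and concomitant medication) and Listings 16.2.3.1.1 to 16.2.3.1.5 (all AEs, SAEs, deaths, AEs leading to drug discontinuation, AESIs).

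5. **Outputs not reached.** Table 14.1.1 and Listing 16.2.1.1 (disposition and reason) and Listing 16.2.3.5 (C-SSRS) use the Randomized Population. Table 14.1.4 (exposure and compliance) uses ITT.

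6. **What could count as a measurement.**
   - *Any AE record.* SAP 5.4.1 lists AEs among the safety variables, SAP 7.9 names them first among the ways safety is assessed, and protocol 5.4 includes them in the safety assessments. This is the ordinary reading.
   - *Anything done after randomisation, even before dosing.* Protocol 4.2.3 lists randomisation at Visit 3 as item 4, the safety scales, bloods and C-SSRS as items 7, 9 and 11, and dispensing as item 14. If sites work in that order, pre-dose assessments satisfy the clause and it removes almost nobody.
   - *Only scheduled post-dose assessments such as scales, ECG or C-SSRS.* The first of these is Visit 4, 7 ± 2 days after Visit 3. This reading removes the most children.

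7. **Effect on an incidence.** Let an arm have N dosed children, e of them with the event, and let the clause remove m children, k of them with the event. The incidence moves from e/N to (e − k)/(N − m).
   - If an AE record qualifies, k = 0 for AE tables. The result is e/(N − m), slightly higher than e/N.
   - If only scheduled assessments qualify, k can exceed 0. The reported incidence falls whenever k/m is greater than e/N, that is, when the removed children had the event more often than the arm as a whole.
   - The effect on the comparison between arms depends on how m and k split by arm. The documents give neither.

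**The case against.** The strongest reply is that the affected group is nearly empty. Protocol 4.2.3 has a post-dose AE enquiry at Visit 3. Protocol 4.2.7 and 4.6 send early discontinuers to Visit 7, which covers safety scales, vital signs, laboratory tests, C-SSRS and AEs. Protocol 4.2 has every child who took study medication followed unless consent to follow-up is withdrawn. This stands as an argument about size. It does not make the group empty by design: withdrawn consent and loss to follow-up are both planned discontinuation categories (protocol 6.5), and protocol 4.3.1 has treatment begun after noon start with the evening dose, so the first tablet may follow the Visit 3 enquiry.

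Four stronger readings are tempting, and the documents do not support them.

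- *A child whose reaction was phoned in vanishes from the safety data.* This needs a reading in which a recorded AE is not a safety measurement, against SAP 5.4.1, SAP 7.9 and protocol 5.4. It is possible only because the term is undefined.
- *The child is in no discontinuation table.* Table 14.1.1 is on the Randomized Population, with adverse event among the reasons. Only the table of TEAEs leading to discontinuation (14.3.1.8) is lost. On the narrow reading the two tables could disagree.
- *The loss can be expressed as a percentage, or consists mainly of early extrapyramidal events.* The documents give no count of such children and no timing for those events.
- *No treatment-assignment rule exists for safety.* SAP 7.1.1 states none, but protocol 6.3 says the populations follow randomised treatment received. That wording could be clearer, but it is a separate matter.

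**Conclusion.** The mismatch is certain on the wording. SAP 7.1.1 adds a condition that the protocol lacks, SAP 3.6 does not declare it, and by both documents' precedence rule it governs every Table 14.3.x and the AE, SAE, death and AESI listings.

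The size is unknown and probably small. On the ordinary reading the main effect is a slightly smaller denominator. Loss of events requires the narrow reading. The point does not show that the safety comparison is biased in a known direction.

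It is still worth correcting. The clause either removes almost nobody, in which case it serves no purpose, or it selects on follow-up after dosing, in which case it should not be there.

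**What to change.** Delete the added clause from SAP 7.1.1, so that the Safety Population is all randomised subjects who took at least one dose, as in the protocol synopsis and 6.3. Footnote the safety tables with the number of dosed subjects per arm who have no post-dose safety data, so that readers can see how much of each denominator rests on no observation.

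The cost is one sentence in the SAP and one footnote. A few children with no post-dose data stay in the denominators, and the footnote makes this visible.

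If the sponsor prefers to keep the condition, it should be declared and justified in SAP 3.6, with the qualifying measurement defined (including whether any AE record counts and whether it must follow dosing) and the excluded dosed subjects listed by arm.
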